15.5 Analysis of Exploratory Endpoints

The exploratory analyses are not powered for statistical significance.

Potentially, markers of MCs and eosinophils and inflammatory response in blood for each active treatment group will be compared separately with the placebo group, with suitable analyses that will be described in the SAP.

Enrollment in this study is designed for presence or absence of asthma as a stratification factor; thus, asthma will be equally distributed among the 3 groups. This stratification factor may be used in the analyses of the primary and secondary analyses described above. Additional exploratory analyses are planned to explore any possible trend in favor of AK001 in the subgroup of asthmatic patients.

In patients with comorbid asthma, use of asthma rescue therapy will be summarized by number and percentage. Changes from Baseline; percentage changes from Baseline; absolute TPS (Appendix 2 [Section 19.2](#)); pulmonary function (assessed using spirometry) as evaluated by FEV1, FVC, FEF; and ACT (Appendix 8 [Section 19.8](#)) for each active treatment group will be compared separately with the placebo group using the same repeated measures model described above, to detect any potential trend at Week 12 and at other visits.

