--	--

STUDY DESIGN
	
This is a Phase 2, randomized, double-blind, placebo-controlled study of the safety and tolerability of AK001 compared with placebo in patients with moderate to severe chronic nasal polyposis and whose symptoms are resistant to treatment with INSs. At least 50% of patients enrolled will have comorbid asthma.
 
The study will comprise an up to 4-week Screening period and a 4-week Run-in period followed by randomization and dosing with AK001 or placebo for 7 weeks followed by a 17-week observation (Post-treatment) period. There will be 10 scheduled study visits. The total duration of the study will be up to approximately 32 weeks.
 
After the Screening period, approximately 70 eligible patients will be enrolled and enter a Run-in period of 4 weeks to achieve a stable regimen with a common intranasal topical steroid (NASONEX [mometasone furoate monohydrate] 2 sprays in each nostril twice a day) and discontinue any other intranasal topical steroid. Patients will return to the clinic at the end of the Run-in period prior to dosing with study drug for pre-dose evaluations. Patients who continue to meet the eligibility criteria for the study will be randomized, will continue to use NASONEX until the end of the study, and will also receive either 25 mg of AK001 (n=25), 250 mg of AK001 (n=25), or a corresponding placebo (n=20) on Days 0, 21, and 49. The randomization will be stratified based on presence or absence of asthma. Patients will be required to maintain their Baseline treatments for nasal polyposis unchanged throughout participation in this trial.
 
Enrollment will be staggered; no more than 1 patient will be randomized every 4 weeks at each site.
 
If there are any safety concerns, enrollment will be put on hold, and a safety review meeting will occur.
 
A Data Monitoring Committee will be convened periodically to monitor the safety of patients over the course of the study.

PRIMARY OBJECTIVE
	
To evaluate the effect of 2 different dose levels of AK001 in combination with an INS versus the INS alone on the reduction in size of nasal polyps as evaluated by the change from Baseline to Week 12 after the start of treatment in Total Polyp Score (TPS)

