4.1 Study Overview

This is a Phase 2, randomized, double-blind, placebo-controlled study of the safety and tolerability of 2 different dose levels of AK001 compared with placebo in combination with an INS in patients with moderate to severe chronic nasal polyposis and whose symptoms are resistant to treatment with INSs. At least 50% of patients enrolled will have comorbid asthma.

As presented in [Figure 1](#), the study will comprise an up to 4-week Screening period and a 4-week Run-in period followed by randomization and dosing with AK001 or placebo for 7 weeks followed by a 17-week observation (Post-treatment) period. There will be 10 scheduled study visits. The total duration of the study will be up to approximately 32 weeks.

After the Screening period, which will last up to 4 weeks, approximately 70 eligible patients will be enrolled and enter a Run-in period of 4 weeks to achieve a stable regimen with a common intranasal topical steroid (NASONEX; [mometasone furoate monohydrate] 2 sprays in each nostril twice a day) and discontinue any other intranasal topical steroid. Patients will return to the clinic at the end of the Run-in period prior to dosing with study drug for pre-dose evaluations. Patients who continue to meet the eligibility criteria for the study will be randomized, will continue to use NASONEX until the end of the study, and will also receive 25 mg of AK001 (n=25), 250 mg of AK001 (n=25), or a corresponding placebo (n=20) on Days 0, 21, and 49. Patients will be required to maintain their Baseline treatments for nasal polyposis unchanged throughout participation in this trial.

Figure 1 Study Schema

A Data Monitoring Committee (DMC) will be convened periodically to monitor the safety of patients over the course of the study. Members of the DMC can request the identities of patients’ study drugs if needed. Additional information about the DMC can be found in the DMC charter.

Enrollment will be staggered; no more than 1 patient will be randomized every 4 weeks at each site.

If there are any safety concerns, enrollment will be put on hold, and a safety review meeting will occur.

The schedule of the required evaluations is provided in [Table 1](#).

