15.3 Analysis of Primary Endpoint

The effect of 2 different dose levels of AK001 in combination with an INS versus the INS alone on the reduction in size of nasal polyps as evaluated by the change from Baseline to

Week 12 after the start of treatment in TPS (Appendix 2 [Section 19.2](#)) will be displayed for each treatment group by study visit using summary statistics, including the number of observations, the mean, median, standard deviation (SD), and range. Each active treatment group will be compared separately with the placebo group for change from Baseline in TPS by using a mixed effect repeated measures analysis of variance (ANOVA) model with specific contrast statement for Week 12 and for each comparison separately. Adjustment in alpha for multiple comparisons will be controlled according to the Hochberg method, in which, if the efficacy comparison of the high active arm versus placebo is statistically significant at the 0.05 level, no penalty will be assessed to the comparison of the low active arm versus the placebo arm. Otherwise, the low active arm versus the placebo arm will be compared at the 0.025 level.

Missing values for the primary endpoint will be imputed by 2 methods: last observation carried forward and worst observation carried forward. Imputations will be done on the total score level and not on the individual item level. Due to the sample size, no multiple imputation technique is intended.

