15.4 Analysis of Secondary Endpoints

Additional efficacy measures will be analyzed in support of the primary efficacy endpoint results.

In addition to change from Baseline in TPS (Appendix 2 [Section 19.2](#)), absolute values and percentage changes from Baseline will be analyzed separately using the same repeated measures model described above. A responder analysis will also be considered. The response definition and its appropriate analysis methodology will be presented in the SAP. The numbers (percentages) of patients who are responders and time to first response for each active treatment group will be compared separately with the placebo group, if feasible.

Examination of the treatment effect over time for TPS (Appendix 2 [Section 19.2](#)), UPSIT (Appendix 4 [Section 19.4](#)), and patient-reported symptoms of sinusitis (SNOT-22) (Appendix 5 [Section 19.5](#)) will be examined using an appropriate similar repeated measures ANOVA. The stratification factor, presence or absence of asthma, may be included in the model. The details of the analytical methods will be presented in the SAP.

Size of polyps as evaluated by Lund-Mackay score (Appendix 3 [Section 19.3](#)) at selected Investigator sites by CT scan (CT scans are optional and will only be done at Investigator sites at which appropriate and timely regulatory approval or authorization can be granted); PNIF; UPSIT (Appendix 4 [Section 19.4](#)); and patient-reported SNOT-22 (Appendix 5 [Section 19.5](#)), VAS (Appendix 6 [Section 19.6](#)), clinical symptoms improvement scale³ (Appendix 6 [Section 19.6](#)), and SF-36 (Appendix 7 [Section 19.7](#)) scores for each active treatment group will be compared separately with the placebo group using a repeated measure ANOVA with contrast statements for comparison at Week 12 as well as other time points in the study.

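### Randomisation is stratified by asthma, but the primary TPS model may or may not include the stratum; fixing the term is a small, nearly free gain

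*Protocol*

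**What the plan says.** The synopsis sets the design: "The randomization will be stratified based on presence or absence of asthma". Section 8.1 repeats it, and 4.1 adds "At least 50% of patients enrolled will have comorbid asthma".

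Section 15.3 compares each active arm with placebo "for change from Baseline in TPS by using a mixed effect repeated measures analysis of variance (ANOVA) model with specific contrast statement" for Week 12. It names no covariate and no stratum.

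Section 15.4 (and the synopsis) says of the treatment-over-time models for TPS, UPSIT and SNOT-22: "The stratification factor, presence or absence of asthma, may be included in the model". The same section carries the primary model over to other TPS scales: "absolute values and percentage changes from Baseline will be analyzed separately using the same repeated measures model described above".

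The stratum's role in the primary analysis appears only in 15.5, under exploratory endpoints: "This stratification factor may be used in the analyses of the primary and secondary analyses described above". That section also says "thus, asthma will be equally distributed among the 3 groups", and it applies the model to the asthma-only analyses, "using the same repeated measures model described above, to detect any potential trend at Week 12 and at other visits".

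No section makes the term mandatory or gives a rule for deciding. Section 15 requires the SAP to be completed before unblinding.

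**The concern.** An analysis should reflect the factor by which the trial randomises. Stratification makes the arms alike in asthma, so the true sampling error of the treatment difference is smaller. A model without asthma does not know this. It leaves the between-stratum variance in the residual and reports a standard error that is too large. Balance across the arms, which 15.5 relies on, protects against bias but does not give this precision back.

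At stake are confidence intervals somewhat too wide and a test below its nominal level, in a trial of about 70 patients. False-positive inflation is not at stake. Nor is data-driven model choice, because the SAP is fixed before unblinding.

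**Working it through.** **Inputs from the protocol.** Arms of 25, 25 and 20; mean change -1.9 (active) and -0.3 (placebo), a difference of 1.6; SDs 2.064 and 1.128; alpha 0.05 (all 15.7); asthma share at least 50% (4.1). **Assumed.** Two-sided testing, the strength of asthma as a predictor, and permuted blocks of 14.

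**1. The stated power.** SE = √(1.128²/20 + 2.064²/25) = √(0.0636 + 0.1704) = 0.484, and 1.6/0.484 = 3.31. With Welch df of 38.5, power is 89.7%. A two-arm pooled t-test (SD 1.715) gives 86.0%. The plan's figure of at least 80% is met.

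**2. What the stratum explains.** Let p be the asthma share and s the asthma shift in within-stratum SDs. The share of within-arm variance explained is R² = p(1-p)s² / [1 + p(1-p)s²]. For p = 0.5 and s = 0.3, 0.6, 1.0 this is 2.2%, 8.3% and 20%. In units of the total SD, the SE without the term is √(1/25 + 1/20) = 0.300. With it, 0.300·√(1-R²) = 0.297, 0.287 and 0.268, or about 1%, 4% and 11% smaller.

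**3. Equal arm SDs.** Simulation of a three-arm linear model at Week 12, high dose against placebo, with 35 patients in each stratum and 40,000 runs per cell. The effect is 1.6/√[(1.128² + 2.064²)/2] = 0.962 total SD.

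| Shift (within-stratum SD) | Type I error without / with | Power without / with | Gain (points) |
|---|---|---|---|
| 0 | 0.050 / 0.051 | 0.885 / 0.885 | 0 |
| 0.3 | 0.048 / 0.050 | 0.887 / 0.891 | 0.4 |
| 0.6 | 0.041 / 0.050 | 0.890 / 0.907 | 1.7 |
| 1.0 | 0.030 / 0.052 | 0.904 / 0.940 | 3.7 |

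With a 42/28 split the gains are similar: 0.4, 1.6 and 3.4 points.

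**4. Arm SDs as in 15.7.** Same model with pooled variance, shift in TPS points, 20,000 runs.

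| Shift (TPS points) | Type I error without / with | Power without / with | Gain (points) |
|---|---|---|---|
| 0 | 0.027 / 0.026 | 0.839 / 0.839 | 0 |
| 0.3 | 0.025 / 0.025 | 0.843 / 0.845 | 0.2 |
| 0.6 | 0.026 / 0.028 | 0.846 / 0.853 | 0.7 |
| 1.0 | 0.021 / 0.024 | 0.853 / 0.876 | 2.3 |

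Here the test is already conservative for another reason. The pooled variance is (19·1.272 + 48·4.260)/67 = 3.413, so the model SE is √(3.413·0.09) = 0.554 against a true 0.484. The stratum term does not cure that.

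**5. Cross-check and cost.** In the Welch calculation, multiply the residual variance by (1-R²) and remove one df (38.5 to 37.5).

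- R² = 0: power goes from 89.69% to 89.65%, a loss under 0.1 point.
- R² = 2%, 5%, 10% (asthma differences of about 0.5, 0.8 and 1.1 TPS points): 90.2%, 91.1% and 92.5%, gains of 0.5, 1.4 and 2.8 points.
- At 0.025, the level for the low dose if the high dose fails: from 83.1% to 83.8%, 85.0% and 87.0%.

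A separate simulation with the SDs of 15.7 and near-exact asthma balance in every arm moved power from 84.4% to 85.4%, 84.2% to 86.4% and 84.6% to 88.4% at those R² values. Its gains exceed those in step 4 because incomplete blocks there leave some chance imbalance.

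**The case against.** The strongest reply is that model terms belong in the SAP. Section 15 defers full detail to it, 15.4 follows its permissive sentence with a similar deferral, and the SAP is fixed before unblinding. On that reading nothing is wrong, only unfinished. This rules out any charge of post-hoc choice. It does not remove the point, because the protocol is not silent: it takes up the stratum's place in the primary analysis, makes it discretionary, and does so under exploratory endpoints.

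Several limits on the size do stand.

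- The prognostic strength of asthma is not in the protocol. The background calls patients with asthma poor responders but gives no figure for TPS change, and nothing supports the upper end of the range.
- With the SDs of 15.7 the gain is smaller, and unequal variances cause most of the conservatism.
- The simulations use one visit, whereas the plan is a repeated-measures model. One degree of freedom buys a main effect only. If the asthma effect varies by visit, a main effect captures part of the gain, and a stratum-by-visit term costs more.
- Asthma prevalence has no ceiling. At a given shift the gain shrinks as prevalence moves well above 60%.
- No gain was computed for UPSIT or SNOT-22.

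None of these reverses the direction.

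**Conclusion.** The concern holds as a minor point worth considering. The protocol stratifies by asthma and then allows a primary model that ignores it. Across the assumed shifts, including the term is worth 0.2 to 2.3 points of power with the SDs of 15.7, and 0.4 to 3.7 points with equal SDs. With equal SDs it also brings the test back to about 5%; with the planned SDs and a pooled variance it does not. If asthma is not prognostic there is no gain and no measurable loss. Power stays above 80% in every case examined. The direction is secure. The size depends on the assumed asthma effect, two-sided testing, the assumed block size and a single-visit approximation.

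**What to change.** Add to 15.3: *The primary repeated-measures model will include the randomisation stratum (asthma present or absent) as a fixed effect.* This also settles the absolute and percentage TPS analyses in 15.4, which reuse the model. Replace the permissive wording with *will* in 15.4, 15.5 and the synopsis. State that the term is dropped from the asthma-only analyses in 15.5, where it is constant. If the SAP already includes the term, align the protocol with it.

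The cost is a few words and one degree of freedom for the main effect. No new data, visits or patients are needed.

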15.6 Safety Analysis

Safety and tolerability will be assessed throughout the study by monitoring and evaluating TEAEs, including any complications resulting from the IV infusion, and changes in vital signs and in clinical safety laboratory test (including ADA) and PE findings. All safety and tolerability endpoints will be summarized by treatment. Baseline for all safety endpoints will be defined as the last recorded observation before the administration of the IV infusion of study drug. Safety measures, including AEs, clinical safety laboratory tests (including ADA), vital signs, PEs, and concomitant medication usage, will be summarized descriptively. For quantitative variables, descriptive statistics, including number of observations, means, medians, SDs, and ranges, will be provided for the values themselves as well as for the changes from Baseline by treatment group at each study visit. Qualitative variables will be summarized using counts and percentages in each treatment group at each study visit.

Adverse Events:

All AEs will be coded using the latest version of the Medical Dictionary for Regulatory Activities (MedDRA) and will be classified by MedDRA system organ class (SOC) and preferred term. The summaries of AEs will be based on TEAEs. A TEAE is defined as an AE reported in the clinical database with a date of onset (or worsening) on or after the start date of study drug through the end of the study.

The following information will be presented for AEs:

- TEAEs by SOC and preferred term
- TEAEs by maximum severity, SOC, and preferred term
- Drug-related TEAEs by SOC and preferred term
- TEAEs leading to withdrawal by SOC and preferred term
- Serious TEAEs by SOC and preferred term

All AEs will be collected starting from the first study drug administration through Day 168 or ET. Severity will be assessed by the Investigator using the protocol-defined grading scales (Section 11.1). All AEs will also be judged by the Investigator as to whether they are clinically significant and related to study drug.

Vital Signs:

Body temperature, supine systolic and diastolic blood pressure, pulse, and respiratory rate will be measured at Screening and on Days -3, 0, 14, 21, 49, 84, 112, and 168 or ET. On Days 0, 21, and 49, vital signs will be measured pre-dose, every 15 minutes after the start of infusion, and immediately following the end of infusion. All vital signs will be measured after the patient has been in the supine position for ≥ 5 minutes.

Descriptive statistics will be used to summarize vital signs at Baseline, each visit and time point, and the change from Baseline for each visit and time point.

Laboratory Assessments:

Samples will be obtained for the clinical safety laboratory tests (hematology, chemistry, urinalysis) and for ADA specified in Table 1 and Sections 9.3.2, 9.3.3, 9.3.5, and 9.4.

Descriptive statistics will be used to summarize laboratory results at Baseline, each visit, and the change from Baseline for each visit. In addition, shift tables will summarize the laboratory results relative to normal reference ranges at Baseline and each post-baseline time point.

Physical Examinations:

A complete PE will be performed at Screening, and symptom-directed PEs will be performed pre-dose (and post-dose as indicated) on Days 0, 21, and 49 and on Days 14, 21, 84, 112, and 168 or ET. Shift tables will summarize the examination results as normal or abnormal at Baseline and at the end of study.

Prior and Concomitant Medications:

All medications (prior and current) will be coded using the latest version of the World Health Organization Anatomical Therapeutic Chemical (ATC) Classification System. Concomitant medications will be summarized by ATC Class 1, ATC Class 3, and preferred term.

15.7 Sample Size and Randomization

The study will be conducted at approximately 14 investigational sites in the European Union and the United States, and approximately 70 patients will be enrolled.

This study will evaluate the effect of 2 different dose levels of AK001 in combination with an INS versus the INS plus placebo on the reduction in size of nasal polyps. Assuming equal efficacy effect of the 2 active treatment arms, a planned sample size of approximately 70 patients (25 mg of AK001 [n=25], 250 mg of AK001 [n=25], and a corresponding placebo (n=20)) will ensure at least 80% power to detect a difference in mean nasal polyp scores between the placebo group (Mean= -0.3; SD ≤ 1.128) and each of the AK001 groups (Mean= -1.9; SD ≤ 2.064) with an alpha of 0.05. PASS 11, Version 11.0.10, was used for this power analysis.

15.8 Interim Monitoring

No interim analyses are planned for evaluating efficacy. However interim safety monitoring will be performed according to the DMC charter.

16 DATA COLLECTION, RETENTION, AND MONITORING

16.1 Data Collection Instruments

All staff at each investigational site will adhere to Good Documentation Practices. Data will be entered into eCRFs using source document data. Source documents may include, but are not limited to, laboratory data, recorded data from automated instruments, medical progress notes, and email correspondence.

16.2 Data Management Procedures

The data will be entered into a validated database. The Data Management group will be responsible for data processing in accordance with procedural documentation. Database lock will occur once quality assurance procedures have been completed.

All procedures for the handling and analysis of data will be conducted using good computing practices that meet FDA and local applicable authority guidelines for the handling and analysis of data for clinical trials.

16.3 Data Quality Control and Reporting

After data have been entered into the study database, a system of computerized data validation checks will be implemented and applied to the database on a regular basis. Queries are entered, tracked, and resolved through the electronic data capture system directly. The study database will be updated in accordance with the resolved queries. All changes to the study database will be documented.

16.4 Archiving of Data

The database is safeguarded against unauthorized access by established security procedures; appropriate backup copies of the database and related software files will be maintained. Databases are backed up by the database administrator in conjunction with any updates or changes to the database.

At critical junctures of the protocol (e.g., production of interim reports and final reports), data for analysis is locked and cleaned per established procedures.

16.5 Availability and Retention of Investigational Records

In accordance with 21 CFR 312.62(c) and ICH/GCP 4.9.5 and all other applicable regulatory requirements, following completion or termination of the study, the investigational sites will retain a copy of all study records in a limited-access storage room for a minimum of 2 years after notification that the investigations have been discontinued and the FDA has been notified or for 2 years after all marketing applications have been

approved. The Trial Master File will be created during the implementation phase of a study, maintained on an ongoing basis throughout the duration of the project, and collated at the end of the study. The files will contain folders that may include, but are not limited to, the following sub-categories:

- Financial agreements
- Regulatory documents
- IRB/IEC documents
- Drug accountability
- Correspondence
- Medical reports
- Patient data
- Monitoring visit reports
- Sample eCRFs and eCRF guidelines

